Coagulation (PT/PTT) and Hb A1C	X									
Research blood draw	X		X		X				X	
CT of Abdomen and Pelvis. /CT urogram/MRI abdomen and pelvis/PET ^{9, 13,15}	X				X				X	
Bone scan ^{9, 13,15}	X				X				X	
Chest Imaging ^{9,15}	X								X	
Pacritinib dispense	X ⁷		X ⁷	X	X	X ⁷	X ⁷		X	
Patient-reported outcome instrument: - FACT-P	X					X				

1. All screening procedures must occur within 30 days prior to treatment initiation.
2. Day 1 assessments are required to be performed prior to initiation of study treatment and can be performed up to 24 hours prior to initiation of study treatment. Study days are to be counted based on the start of treatment.
3. If a subject has disease progression or subject withdrawal, then they will be followed as per follow-up requirements. Patients will be in follow up for 2 years from EOT visit.
4. Vital signs include systolic and diastolic blood pressure, pulse, respiratory rate, temperature, and body weight.
5. A 12-lead ECG (collected in triplicate), including QTcF, will be performed at Screening, and then predose at C1D1, C2D1,, C5D1, C7D1, and every four months (every other cycle/odd cycles) thereafter provided normal QTcF.. if QTc is prolonged, more frequent monitoring will be done after discussion with sponsor. For patients who have discontinued treatment, ECGs are to be performed at the End-of-Treatment Visit but are not otherwise required
6. TTE will be performed at screening, C2D1, C5D1, C8D1, and every six months thereafter (every 3 cycles) provided normal LVEF and no

clinical evidence of heart failure. Window for all TTEs is -14 days from Day 1 of the cycle it is due for.

7. On days when ECGs are to be obtained, Pacritinib will be administered in the clinic to facilitate the performance of pre-dose assessments
8. Serum chemistry values will include AL T/SGPT, AST/SGOT, alkaline phosphatase, bilirubin (total, direct, and indirect) creatinine, LDH, sodium, potassium, chloride, bicarbonate, calcium, phosphate, magnesium, BUN/urea, albumin, glucose, cholesterol (fasting not required), and uric acid. Serum chemistry results obtained from unscheduled visits should be entered into the electronic database.
9. Additional serum chemistry testing should be done as clinically indicated.

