4.1 Subject Status

Subject statuses throughout the trial are defined as follows:

- Prescreening: preconsent (subject considering trial or study staff considering a patient for the trial per institutional recruitment methods).
- Screening: the period after the consent, but prior to eligibility confirmation.
- Consented: consented, prior to eligibility confirmation.
- Eligible: the local investigator confirms all eligibility criteria apply.
- On study/enrolled: date eligibility is confirmed.
- On arm: date of enrollment.
- On treatment: first-day treatment was given to the last day treatment was given.
- Off treatment: the last day treatment was given.
- On follow-up: from the last day of treatment to the end of the follow-up period.
- Off study: follow-up period completed, with no additional data gathered.
- Withdrawn: subject fully withdraws consent (i.e., refuses ALL follow-up, even survival) or is taken off the study by the local principal investigator.

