4.6 Discontinuation of Study Treatment, Withdrawal, and Compliance

Treatment duration is 2 years. Patients may continue drug beyond two years if, in the opinion of the treating physician, the patient is benefitting from treatment and benefits outweigh any risks of therapy

Discontinuation from the study treatment does not mean discontinuation from the study. The subject will be considered in follow-up, study procedures should still be completed as indicated by the study protocol, and AEs/SAEs will continue to be reported according to this protocol.

In the absence of treatment delays due to adverse events, study treatment/intervention may continue until:

- Disease progression per PCWG3 guidelines
- General or specific changes in the subject's condition renders the subject unacceptable for further treatment in the investigator's judgment.
- An inter-current illness that prevents further treatment administration.
- The subject decides to withdraw from the study.
- The subject has significant noncompliance with the protocol (see below).
- Unacceptable adverse event(s) and/or dose level reduction beyond requirements as detailed in this protocol.
- The clinical need for concomitant therapy that is not permitted in the study.
- Subjects who sign the informed consent form, enroll and receive the study intervention, but subsequently withdraw, or are withdrawn or discontinued from the study will not be replaced.

Progression of disease

Progression of disease per PCWG3 is defined as one or more of the following:

PSA progression

Recognize that a favorable effect on PSA may be delayed for \geq 12 weeks, even for a cytotoxic drug. Monitor PSA by cycle but plan to continue through early rises for a minimum of 12 weeks unless other evidence of progression.

If there is a decline in PSA from baseline: record time from baseline to the first PSA increase that is $\geq 25\%$ and ≥ 2 ng/mL above the nadir, and which is confirmed by a second value ≥ 3 weeks later (i.e., a confirmed rising trend).

If there is no decline in PSA from baseline but stable PSA at 12 weeks: PSA progression will be defined as $\geq 25\%$ and ≥ 2 ng/mL from PSA at 12 weeks .

Radiographic progression

Radiographic progression will be assessed per RECIST 1.1. Any new unequivocal bone lesion is considered progression, except if that lesion appears in the first post-treatment scan; in that

case, document the event, continue treatment until two additional new lesions appear, and record both events.

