
Consent Withdrawal

A subject may decide to withdraw from the study at any time. MCWCC CTO will follow their IRB of record's SOPs regarding consent withdrawal.

If a subject intends on withdrawing consent, staff should confirm which of the following options the subject chooses and document the discussion:

- Full consent withdrawal, with no study follow-up.
- Selective consent withdrawal from the interventional portion of the study but agree to continued follow-up of associated clinical outcome information.

Investigator-initiated Withdrawal

The investigator will withdraw a subject whenever continued participation is no longer in the subject's best interests. Reasons for withdrawing a subject include, but are not limited to, disease progression, the occurrence of an adverse event or a concurrent illness, a subject's request to end participation, a subject's noncompliance, or simply significant uncertainty on the part of the investigator that continued participation is prudent. The reason for study withdrawal and the date the subject was removed from the study must be documented.

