3	
Hold treatment.If the toxicity resolves to grade ≤ 1 or the baseline grade within seven days, treatment may be resumed at the same level or the next lower dosage. Concomitant antidiarrheal treatment is required for patients restarting pacritinib at the 100 mg QD dosage level.If the toxicity recurs after the restart at the same dosage level, treatment may only be resumed at the next lower dosage level.If the toxicity resolves to grade ≤ 1 or the baseline grade after more than seven days, treatment may be resumed only at the next lower dosage level. Discontinuation is required if on hold from the 100 mg QD dosage level. Concomitant antidiarrheal treatment is required for patients restarting pacritinib at the 100 mg QD dosage level.

CTCAE v5 Toxicity Grade	Management/Action
	
 If the toxicity recurs after the restart at the lower dosage level, pacritinib treatment must be discontinued.
4	
 Discontinue pacritinib

5.2.5 Pacritinib Dosage Management Guidelines for Pacritinib-Related Nonhematologic Toxicities Other than QTc Prolongation, Decreased Cardiac Ejection Fraction, Other Cardiac Toxicities or Diarrhea

As defined in Table 5, a maximum of two dosage reductions are allowed for pacritinib-related nonhematologic toxicities other than QTc prolongation, decreased cardiac ejection fraction, or diarrhea.

Table 5. Treatment Toxicity and Dosage Management: Pacritinib-Related Nonhematologic Toxicities Other than QTc Prolongation, Decreased Cardiac Ejection Fraction, Other Cardiac Toxicities or nausea, vomiting and Diarrhea

CTCAE v5 Toxicity Grade	Management/Action
1 or 2	No change.
3	
 Hold treatment. If the toxicity resolves to grade ≤ 1 or to the baseline grade within seven days, treatment may be resumed at the same level or the next lower dosage, at the discretion of the investigator after discussion with the Sponsor. Toxicity that does not resolve to grade <1 or to the baseline grade within seven days requires dosage reduction to the next lower dosage.
4	
 Hold treatment. If the toxicity resolves to grade <1 or to the baseline grade within seven days, treatment may be resumed, but the dosage will be reduced by one dosage from the level at which the toxicity was observed. If grade 4 toxicity occurs at the lowest dosage of 100 mg QD, the patient should be discontinued from the study.

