8.10 Missing data

For all outcomes, summary statistics will include the count of missing and non-missing values. Patients with missing value for the primary outcome, PFS, will be censored at the time when last known to be alive and without progression. A similar approach will be used for other time-to-event outcomes, such as time to PSA nadir. Secondary outcomes requiring numeric values, such as geriatric assessments, PSA and testosterone levels will be analyzed among patients with non-missing values as required for each analysis (e.g., non-missing value at specific time point for cross-sectional analysis, and non-missing values at two time points for change analyses). The limitations of extensive missingness, if present, will be clearly noted in all reports and any related findings will be interpreted with caution.

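### Section 4.6 keeps men who stop treatment in follow-up, yet also lists the same events as grounds for the investigator to remove them from the study, so PSA and next-therapy data can be lost

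*Combined protocol and SAP*

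**What the plan says.** Section 4.6 opens with a clear principle: "Discontinuation from the study treatment does not mean discontinuation from the study". The man moves to follow-up and study procedures carry on.

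Later in the same section, under investigator-initiated withdrawal, the operative rule is: "The investigator will withdraw a subject whenever continued participation is no longer in the subject's best interests". The examples follow: "Reasons for withdrawing a subject include, but are not limited to, disease progression, the occurrence of an adverse event or a concurrent illness", and then noncompliance among others. This is withdrawal from the study and not only from the drug, because staff must record it as such: "The reason for study withdrawal and the date the subject was removed from the study must be documented".

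Four other places bear on it:

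- Section 4.1 defines the Withdrawn status as full refusal of follow-up, survival included, or a subject who "is taken off the study by the local principal investigator".
- Table 5 (Section 5.2.5) says of grade 4 toxicity at the lowest dosage that "the patient should be discontinued from the study".
- Study calendar footnote 3 points the other way: "If a subject has disease progression or subject withdrawal, then they will be followed as per follow-up requirements". Follow-up lasts two years from the end-of-treatment visit.
- Section 8.10 says that a patient whose primary outcome is missing "will be censored at the time when last known to be alive and without progression". Section 4.6 adds that withdrawn subjects are not replaced.

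**The concern.** Progression, intercurrent illness, unacceptable adverse events and noncompliance also appear in Section 4.6 as reasons to stop treatment. One event can therefore lead to either path: off drug with follow-up, or out of the study. Two coordinators reading the same section could handle the same man differently.

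What is lost depends on when removal happens.

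- Before confirmed PSA progression (for example after an adverse event, a concurrent illness, radiographic progression or an unconfirmed PSA rise), the primary endpoint is cut short. Kaplan-Meier then treats the man as having the same outlook as those who remain, which is too favourable if he is likely to progress sooner. In the count of 27 or more among 46 (Section 8.3) he cannot be shown to be progression-free at six months. The two readings of the primary endpoint then move in opposite directions. The same censoring enters the Kaplan-Meier futility look, which rests on ten men plus any enrolled meanwhile.
- After confirmed PSA progression, the primary event is already recorded. The loss is mainly time to next antineoplastic therapy, a secondary endpoint.

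**Working it through.** **The text.** Take a man who stops for an adverse event in month 2 without PSA progression. The opening of Section 4.6 keeps him in follow-up. The withdrawal paragraph with Section 4.1 allows him to be classed with men who refuse all contact, and Section 8.10 then censors him at his last PSA. Footnote 3 names progression and subject withdrawal. It does not clearly cover removal by the investigator for an adverse event, illness or noncompliance.

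**Inputs.** The documents give no removal rate for this trial, so the size can only be bracketed.

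- Plan: N = 46, null 50%, target 66%, success rule 27 of 46 (Sections 8.2 and 8.3). The plan's own conversion reproduces: a 10-month exponential median gives 0.5^(6/10) = 0.660. The gap between null and target is 16 points.
- Assumed share stopping for an adverse event: w = 17.4%, from PAC203 (Section 1.5.4), about 0.174 × 46 = 8 men. A lower value of 5% is also shown. All of these men are taken to be removed from the study.
- Assumed stopping time c: uniform between 0.5 and 4 months.
- Assumed on-treatment median m: 8 or 10 months. Assumed median after stopping p: equal to m (hazard unchanged), 6 months or 3 months.

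**Formulas.** With stoppers censored at c, Kaplan-Meier estimates 0.5^(6/m). The true value is (1 − w) × 0.5^(6/m) + w × A, where A is the average over c of 0.5^(c/m) × 0.5^((6 − c)/p). The bias is therefore w × (0.5^(6/m) − A).

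| w | m | p | Kaplan-Meier | A | True | Bias (points) |
|---|---|---|---|---|---|---|
| 17.4% | 8 | 8 | 0.595 | 0.595 | 0.595 | 0 |
| 17.4% | 8 | 6 | 0.595 | 0.534 | 0.584 | 1.1 |
| 17.4% | 8 | 3 | 0.595 | 0.350 | 0.552 | 4.3 |
| 17.4% | 10 | 10 | 0.660 | 0.660 | 0.660 | 0 |
| 17.4% | 10 | 6 | 0.660 | 0.555 | 0.642 | 1.8 |
| 17.4% | 10 | 3 | 0.660 | 0.365 | 0.608 | 5.1 |
| 5% | 8 | 3 | 0.595 | 0.350 | 0.582 | 1.2 |
| 5% | 10 | 3 | 0.660 | 0.365 | 0.645 | 1.5 |

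**The count.** Documented successes are 46 × (1 − w) × 0.5^(6/m).

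- Hazard unchanged, w = 17.4%: undocumented successes are 46 × 0.174 × 0.5^(6/m), that is 4.0, 4.8 and 5.3 for medians of 6, 8 and 10 months. Kaplan-Meier is unbiased here.
- Post-stop median 3 months, m = 8: 22.6 documented against 25.4 true.
- Post-stop median 3 months, m = 10: 25.1 documented against 28.0 true. Kaplan-Meier reads 66%, at the target, while the expected documented count falls below 27.

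**Would follow-up supply the data?** After the end-of-treatment visit, 30 days after the last dose, the calendar has PSA every six months. A man stopping at month 2 has that visit near month 3 and his next scheduled PSA near month 9, so none falls at month 6. Concomitant medications are recorded only to 30 days after the last dose, and the calendar has no row for subsequent therapy.

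**The case against.** A reader might infer that Section 4.6 obliges investigators to remove every man who progresses or has an adverse event. It does not. The test is the subject's best interests, and the events are examples of reasons. Given the section's opening principle, and follow-up visits only every six months, removal from follow-up might seldom be in question. That stands, and it limits how often the conflict would matter.

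A reader might also infer that about half the men, 23 of 46 at the null rate, would be censored for next therapy at progression. Footnote 3 expressly follows men after progression, so the documents do not support that. Footnote 3 leaves the conflict with the withdrawal paragraph in place, and leaves the other reasons for removal unclear.

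The numerical case is fairly open to attack. The 17.4% is drug discontinuation in myelofibrosis patients after ruxolitinib failure or intolerance, pooled over three dosages, and says nothing about study removal here. The 3-month post-stop median is half the plan's own null median. With 6 months, the bias falls to between 1 and 2 points. These objections bear on the size and leave the contradiction itself untouched.

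Finally, rewording alone would not produce a month-6 PSA or a next-therapy date. That is right, and the fix must cover both.

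**Conclusion.** The concern holds as a contradiction about who stays in follow-up, with a possible but unquantified effect on the primary endpoint. The exposed men are those removed before confirmed PSA progression. Men removed after it keep their primary event and mainly lose time to next therapy.

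If all of an assumed 17.4% were removed, with on-treatment medians of 8 to 10 months, the upward Kaplan-Meier bias is 0 with the hazard unchanged, 1 to 2 points with a post-stop median of 6 months, and 4 to 5 points with 3 months. With 5% removed and the 3-month median it is about 1 to 1.5 points. With the hazard unchanged and 17.4% removed, about 4 to 5 of 46 successes would go undocumented (medians of 6 to 10 months). The removal shares, stopping times and post-stop prognosis are all assumptions.

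The reading that most men who stop would be lost has no support, since no removal rate is given. The point is still worth correcting before more men enter, because PSA values that were never drawn cannot be recovered.

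**What to change.** Reconcile the passages in one amendment:

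1. Section 4.6, investigator-initiated withdrawal: state that the listed reasons concern ending study treatment, and that follow-up continues unless the subject withdraws consent for follow-up.
2. Section 4.1: separate treatment ended by the investigator from the Withdrawn status.
3. Table 5 and calendar footnote 3: align the wording on study participation with items 1 and 2, so that footnote 3 covers men whose treatment ends for any of these reasons.
4. Study calendar: state that men who stop before month 6 without PSA progression keep PSA assessments through month 6.
5. Follow-up visits: record the start of next antineoplastic therapy.

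Items 1 to 3 are wording only. Items 4 and 5 cost a few extra PSA draws (about 8 men at the assumed 17.4%) and one follow-up field. No rule on when to stop the drug changes.

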4.7 Lost to Follow-up

The following actions must be taken if a participant fails to return to the clinic for a required study visit and/or is unable to be reached for follow-up:

- The investigator or designee must make every effort to regain contact and/or reschedule a missed visit with the participant.
- A participant is deemed lost to follow-up if his/her status cannot be obtained after *all* of the following occurs at two consecutive scheduled protocol calendar timepoints:
 - Three telephone calls (at least one day apart) from the study team are unanswered, **AND**
 - A letter (Appendix 2) to the participant's last known mailing address goes unanswered, **AND**
 - These contact attempts must be documented in the participant's medical record or study file.
- Update OnCore® (Follow-up tab and eCRF) when a participant is officially considered lost to follow-up.
- If a subject is considered lost to follow-up, but subsequently contacts the study team, the subject should be considered in follow-up again.

4.8 Accrual Suspension and Closure

The MCW PI facilitates the suspension and closing of accrual in the following manner:

- OnCore® tracks accrual throughout the study.

- If the study must be suspended, OnCore® is updated to ‘suspended’ status.
- When the accrual number is reached, OnCore® notifies staff of study closure.

4.9 End of Study Definition

A participant is considered to have completed the study if he or she completed all phases of the study, including the last visit or the last scheduled procedure shown in the calendar of events or has been discontinued.

4.10 Study Discontinuation and Closure

This study may be temporarily suspended or prematurely terminated if there is sufficient reasonable cause (as determined by the MCW study PI, DSMC, sponsor, and/or IRB). Written notification, documenting the reason for study suspension or termination, will be provided by the suspending or terminating party to study participants, investigator, funding agency, the Investigational New Drug (IND) sponsor, and regulatory authorities. If the study is prematurely terminated or suspended, the MCW principal investigator (PI) will promptly inform the MCW Institutional Review Board (IRB), and the sponsor and will provide the reason(s) for the termination or suspension. Study participants will be contacted, as applicable, and be informed of changes.

5 TREATMENT PLAN

5.1 Pacritinib

5.1.1 Study Treatment Description and Storage

Pacritinib for oral administration is supplied in capsules containing 100 mg (as the free base) in red cap/gray body size 0 opaque hard gelatin capsules. The inactive ingredients are microcrystalline cellulose, magnesium stearate, and polyethylene glycol 8000.

Each capsule contains 146-mg of pacritinib citrate, which is equivalent to 100-mg pacritinib free base. Pacritinib capsules should not be opened or crushed. Direct contact of the powder in pacritinib capsules with the skin or mucous membranes should be avoided. If such contact occurs, affected areas should be washed thoroughly with water. Pacritinib capsules should be stored at controlled room temperature 20°C to 25°C or 68°F to 77°F, with excursions allowed from 15°C to 30°C or 59°F to 86°F. All pacritinib supplies must be kept in a restricted-access area.

5.1.2 Dosage, Route, and Mode of Administration

Patients assigned to pacritinib will be supplied with 100-mg capsules of pacritinib. Patients will take two 100-mg capsules of pacritinib BID, orally, at the same time of day, with or without food. On days when ECGs are to be obtained, pacritinib will be administered in the clinic to facilitate the performance of predose assessments. Any missed or vomited doses should not be retaken or replaced.

Regimen Description				
Study agent	Route	Premedication; precautions	Dose	Duration
Pacritinib	Oral	None	200 mg b.i.d	Continue treatment until progression of disease (at least 12 weeks) or meeting discontinuation criteria.

5.2.2 Dosage Management Guidelines for Hematologic Toxicity and Related Complications

Hematology parameters, including CBC, differential, will be evaluated at regular intervals during the study. These parameters should be monitored more frequently if clinically required. Unscheduled local laboratory test results may be used for the assessment and management of patients in real-time.

Table 1 indicates the required dose interruptions and modifications for hematologic toxicities and complications such as hemorrhage and febrile neutropenia that are treatment related. Of note, if more than one toxicity is experienced simultaneously, the higher-grade toxicity should determine the dose interruption/modification. Treatment-related toxicities are those that are considered at least possibly related to study drug.

Table 1. Treatment Toxicity and Dosage Management: Hematologic Toxicities and Related Complications

Event	CTCAE Grade	Management/Action
Thrombocytopenia	For patients starting treatment with baseline (Day 1) grade 1 thrombocytopenia who have treatment-related ≥ 1 grade decrease in platelets	Hold pacritinib for up to 10 days until recovery of platelet count to grade ≤ 1 or baseline. After recovery, restart at 50% of the prior dose. If thrombocytopenia recurs at the 100 mg BID dose level, discontinue pacritinib.
Hemorrhage	Treatment-emergent hemorrhage Grade 2	Hold pacritinib for up to seven days until hemorrhage resolves. Restart with a 50% dose reduction. If event recurs, discontinue pacritinib
	Grade 3	Discontinue pacritinib.
	Grade 4	Discontinue pacritinib.
Neutropenic infections, including neutropenic sepsis	Grade 2	Hold pacritinib for up to seven days and start at 50% of the dose once

		resolved (100 mg BID). If toxicity recurs discontinue pacritinib
Grade 3		Discontinue pacritinib
Grade 4		Discontinue pacritinib

Coagulation Testing

Coagulation testing will include PT, INR, PTT, at screening. Additional coagulation testing should be done as clinically indicated.

These results will be taken into account, together with baseline platelet counts and prior medical history of bleeding, to help guide ongoing hematologic monitoring of platelet counts and clinical monitoring for bleeding. Pacritinib dosage modifications will be implemented for clinically significant AEs identified with this testing per the guidelines in Table 5.

5.2.3 Pacritinib Dosage Management Guidelines for QTc Interval Prolongation, Reduction in Ejection Fraction, and Other Cardiac Toxicities

A 12-lead ECG (collected in triplicate), including QTcF calculation, will be performed during Screening and at Cycle 1 Day 1, Cycle 2 Day 1, Cycle 5 Day 1, Cycle 7 Day 1, and every four months thereafter provided there is normal QTcF.

Treatment should be modified as shown in Table 2, as recommended by the FDA in case of QTcF interval prolongation. Dose levels referenced in the following tables refer to the following available doses: 200 mg BID, 100 mg BID, and 100 mg QD.

Table 2. Pacritinib-Related QTc Prolongation, Clinically Significant Decreases in Cardiac Ejection Fraction and Other Cardiac Toxicities

CTCAE v5 Toxicity Grade	Management/Action
1	No change.
2 (First occurrence) For patients with grade 2 LVEF decreased at baseline (LVEF 45%-50%) and further decreases in LVEF on the study, see Table 3)	
 Hold pacritinib. If the toxicity resolves to grade ≤ 1 within 14 days, treatment may be resumed at the next lower dosage level (or discontinued, if toxicity occurred while taking 100 mg QD). Toxicity that does not resolve to grade ≤ 1 within 14 days requires treatment discontinuation.
2 (second occurrence)	Discontinue treatment.
3	Discontinue treatment.
4	Discontinue treatment.

Abbreviations: CTCAE = Common Terminology Criteria for Adverse Events; LVEF = left ventricular ejection fraction; QD = once daily; QTc = corrected QT interval.

A transthoracic echocardiogram will be performed at screening, Cycle 2 Day 1, Cycle 5 Day 1, Cycle 8 Day 1, and every six months thereafter provided there is normal LVEF and no clinical evidence of heart failure. The window for all TTEs is -14 days from Day 1 of the cycle it is due at.

Pacritinib dosage modifications will be implemented for clinically significant cardiac ejection fraction changes as per Table 2 and Table 3.

For patients with a grade 2 decreased cardiac ejection fraction at baseline (left ventricular ejection fraction [LVEF]=50% Table 3 should be used for any further decreases in LVEF.

If pacritinib treatment is resumed after holding for ejection fraction abnormality, ejection fraction should be reassessed approximately seven days later, then again within 12 weeks following the seven-day reassessment. If stable, ejection fraction will be checked every six months during the follow-up period and at the End of Treatment Visit. Additional ejection fraction testing shall be done as clinically indicated.

Table 3. Pacritinib-related Clinically Significant Decreased Cardiac Ejection Fraction for Patients with Grade 2 Ejection Fraction (LVEF 45%-50%) at Baseline

CTCAE v5 Toxicity Grade	Management/Action
Worsening of grade 2; 10-19% drop from baseline	Hold pacritinib for one to two weeks and reassess LVEF. If LVEF returns to baseline, the patient may resume treatment at the next lower dose level; if does not resolve, pacritinib should be discontinued.
3	Discontinue treatment.
4	Discontinue treatment.

In patients who resume pacritinib treatment after holding treatment for grade 2 QTc interval prolongation, follow-up ECGs (in triplicate) are recommended on Days 1, 7, 14, 28, and 56 after pacritinib restart. After the restart of pacritinib, QTc monitoring should follow this schedule with ECGs obtained in triplicate:

- Restart Day 1 at four hours (\pm one hour) after ingestion of the first reduced dosage
- Restart Day 7 (\pm two days) four hours after dosing (\pm one hour)
- Restart Day 14 (\pm two days) four hours after dosing (\pm one hour)
- Restart Day 28 (\pm two days) at any time relative to dosing
- Restart Day 56 (\pm seven days) at any time relative to dosing

If grade 2 toxicity does not resolve to grade \leq 1 within seven days, discontinue all treatment with pacritinib. If grade 2 toxicity recurs despite dosage reduction discontinue all treatment with pacritinib. For grade 3 and 4 QTc prolongation, discontinue all treatment with pacritinib.

Other Cardiac Toxicities

Discontinue treatment with pacritinib for all other grade 3 and 4 cardiac toxicities.

